10.2.8.1 Manual Muscle Testing (MMT8)

Manual muscle testing will be performed by trained raters blinded to treatment assignment and who will have no other role or responsibility beyond administering efficacy assessments in the study at the time points specified in the SOE in Section 3.

Manual muscle testing assesses the function and strength of individual muscles and muscle groups based on the effective performance of a movement against gravity or manual resistance. A particular muscle or muscle group is first isolated, then an external force is applied and the patient's ability to complete the movement is graded by a trained therapist or clinician. This study will use an abbreviated MMT, the MMT8 (see Appendix 5), which was developed and validated by IMACS (Rider 2010). In the MMT8, 8 proximal, distal, and axial muscles including the deltoid, biceps, wrist extensors, quadriceps, ankle dorsiflexors, neck flexors, gluteus maximus, and gluteus medius, are evaluated unilaterally. Of note, the 8 muscle groups selected by expert consensus for inclusion in the MMT8 include 4 of the 5 weakest muscles in patients with idiopathic inflammatory myopathies (i.e., the neck flexor, deltoid, gluteus maximus, and gluteus medius) (Harris-Love 2009).

10.2.8.2 Muscle Enzymes

The activity of serum enzymes derived from muscle in myositis patients has long been used as an indicator of myositis disease activity in clinical practice. Collection of blood samples for testing of muscle enzyme levels including CK, ALD, LDH, ALT and AST will be performed at the time points specified in the SOE in Section 3 (see Appendix 6).

10.2.9 Short Form-36 Health Survey

The SF-36 will be completed by the patient at the time points specified in the SOE in Section 3.

The SF-36 is an extensively validated and widely used measure of quality of life that assesses patients' perceptions of health status and its impact on their lives (Ware 1992). It consists of 36 items organized into 8 scales (physical functioning, social functioning, role limitations physical, bodily pain, general medical health, mental health, role limitations emotional, and vitality). Two summary measures of physical and mental health, the Physical Component Summary and Mental Component Summary, respectively, are derived from scale aggregates. Higher scores are associated with better quality of life (see Appendix 7).

10.2.10 Timed Function Tests

The timed function tests will be performed by qualified and trained raters who will be blinded to treatment assignment and study drug injection sites and who will have no other role or responsibility in the study assignment beyond administering these efficacy assessments (see Section 8.4.1) at the time points specified in the SOE in Section 3.

Timed function tests will include time taken to walk/run 10 meters, time taken to stand from a seated position, and time taken to climb 4 standard-sized stairs (Mendell 1989, Griggs 1991, Beenakker 2005, Pradhan 2006, Podsiadlo 1991, Rao 2009) (see the SRM). These tests provide additional measures of muscle strength and functional capability in patients with DM. Decreases in time taken to complete these tasks are considered to be indicative of patient improvement.

10.2.10.1 Timed 10-meter Walk-run Test (10MWR)

This test measures, in seconds, the time it takes a patient to walk as quickly as they can along a marked path without assistance for 10 meters. The time taken to complete the task is measured with a stopwatch.

10.2.10.2 Timed Up and Go (TUG)

This test measures, in seconds, the time taken by an individual to stand up from a standard arm chair, walk a distance of 3 meters, turn, walk back to the chair, and sit down. The time taken to complete the task is measured with a stopwatch.

10.2.10.3 4 Stair Climb Test

This test measures, in seconds, the time it takes the subject to climb up 4 standard-sized steps. The time taken to complete the task is measured with a stopwatch.

10.2.11 5-D Itch Scale (5D Pruritis Scale)

The 5-D Itch Scale will be completed by the patient at the time points specified in the SOE in Section 3.

The 5-D Itch Scale is a brief multidimensional questionnaire for use in clinical trials (see Appendix 8). The five dimensions of itch include degree, duration, direction, disability, and distribution. The duration, degree and direction domains each include one item, while the disability domain has 4 items. All items of these first 4 domains are measured on a 5-point Likert scale. The distribution domain includes 16 potential locations of itch, including 15 body part items and one point of contact with clothing or bandages. The scores of each of the 5 domains are achieved separately and then summed together to obtain a total 5-D score. 5-D scores can potentially range between 5 (no pruritus) and 25 (most severe pruritus).

10.2.12 Clinical Laboratory Tests

Blood and urine samples for routine (Table 7) and safety laboratory (Table 8) tests will be collected at the time points specified in the SOE in Section 3 and analyzed by an accredited central laboratory selected by Idera. The appropriate Laboratory Manual should be referenced for procedures on sample collection, handling, storage, and shipping.

Any value outside of the current reference ranges for the laboratory performing the test will be flagged on the laboratory results. The Investigator will score all abnormal assessment results as either clinically significant (CS), or not clinically significant (NCS). See Section 8.3.2 for guidelines on actions for safety laboratory results.

10.2.12.1 Routine Safety Laboratory Assessments

Table 7. Routine Safety Laboratory Assessments

Category	Analyte
Hematology	CBC: RBC, WBC, hemoglobin, hematocrit, platelet count Differential WBC count: neutrophils, monocytes, lymphocytes, eosinophils, basophils, abnormal cells Absolute cell counts: ANC
Coagulation	PT, activated partial thromboplastin time (aPTT), international normalized ratio (INR)
Clinical chemistry Panel	Renal: Serum sodium, potassium, chloride, bicarbonate, calcium, magnesium, phosphorus, creatinine, urea nitrogen
	Endocrine: Serum glucose, thyroxine (T4), thyroid stimulating hormone (TSH)
	Liver: serum ALT (SGPT), AST (SGOT), LDH, GGT, alkaline phosphatase, albumin, total protein, total bilirubin, direct bilirubin, indirect bilirubin
	Lipids: Serum cholesterol, LDL, HDL
Urinalysis	Routine and microscopic analyses
Hepatitis screen (At Screening Visit only)	Hepatitis B virus (HBV) screen: HBsAg and anti-HBc Hepatitis C virus (HCV) screen: anti-HCV
TB test (within 3 months prior to screening or during the Screening Period)	A negative chest x-ray and one of the following: a) a PPD skin test with \leq 5-mm induration, OR b) a negative (not detected) QuantiFERON result, OR c) a negative T-SPOT.TB test. If the QuantiFERON result is indeterminate, the test may be repeated once (local testing), per Center for Disease Control (CDC) guidelines If the second QuantiFERON test is indeterminate, a PPD skin test may be used to confirm eligibility. (http://www.cdc.gov/tb/topic/testing/default.htm).
Drug abuse (At Screening Visit only)	Urine drug screen

ALT (SGPT) = alanine aminotransferase (serum glutamate-pyruvate transaminase); ANC = absolute neutrophil count; aPTT = activated Partial Thromboplastin Time; AST (SGOT) = aspartate transaminase (serum glutamic oxaloacetic transaminase); CBC = complete blood count; GGT = gamma-glutamyl transferase; HBsAg = hepatitis B surface antigen; HDL = high-density lipoprotein; INR = international normalized ratio; LDH = lactate dehydrogenase; LDL = low density lipoprotein; PPD = purified protein derivative; PT = prothrombin time; RBC = red blood cells; T4 = thyroxine; TB = tuberculin; TSH = thyroid stimulating hormone; WBC = white blood cells

Note: The PPD skin test is not an acceptable method of TB testing in Sweden.

10.2.12.2 Safety Laboratory Assessments

Table 8. Safety Laboratory Assessments

Category	Analyte
Immune activation	Serum globulin, serum albumin, A:G ratio, CRP
Complement activation	C3, C4, CH50
Heart	Troponin

A:G albumin: globulin; C = complement component; CH50 = hemolytic complement activity; CRP = C-reactive protein

10.2.13 12-Lead Electrocardiogram (ECG)

A 12-lead ECG will be obtained at the time points specified in the SOE in Section 3 at the study site. ECGs will be performed only after the patient is positioned supine, resting, and quiet for a minimum of 5 minutes. The ECG will be reviewed and interpreted by medically qualified personnel. The Investigator will review the results of the ECG report, document the interpretation and designate the findings as normal or abnormal (CS or NCS), and report changes from previous readings.

10.2.14 Pregnancy test

Urine samples for pregnancy testing will be collected on all women of childbearing potential at the time points specified in the SOE in Section 3.

Non-childbearing potential is defined as a female who meets *either* of the following criteria:

- Postmenopausal state defined as no menses for 12 months without an alternative medical cause.
- Documented hysterectomy, bilateral tubal ligation or bilateral oophorectomy.

10.2.15 IMO-8400 Plasma Concentration

Blood samples for determination of IMO-8400 plasma concentrations will be collected prior to administration of study drug pre-dose and 2 hours (\pm 15 minutes) post-dose at Visit 2/Week 1, Day 1, Visit 6/Week 5, Visit 14/Week 13, and Visit 22/Week 21. An additional sample will be collected as part of the EOT Visit 26/Week 25 assessments.

If an extension study is initiated and the patient is enrolled, the EOT PK sample will be the same as the Visit 1/Week 1, Day 1 pre-dose sample for the extension study. The appropriate Laboratory Manual should be referenced for procedures on sample collection, handling, storage, and shipping.

10.2.16 Autoantibodies

Blood samples will be collected at the time points specified in the SOE in Section 3 for assessment of autoantibodies associated with idiopathic inflammatory myopathies including, but not necessarily limited to: anti-MDA-5, anti-Mi-2, anti-TIF1 γ , anti-NXP2, anti-SAE1, anti-SAA 60, anti-Ro/SSA 52, anti-SSB/La, anti-Sm, anti-RNP, anti-Scl-70, anti-ribosomal-P, anti-chromatin, anti-Jo-1, anti-PL-7, and anti-PL-12. Assessment of autoantibodies will help to characterize the enrolled population; subgroup analyses may be performed according to the autoantibody profile. Additional serum for anti-platelet antibodies will also be collected at the time points specified in the SOE in Section 3. The appropriate Laboratory Manual should be referenced for procedures on sample collection, handling, storage and shipping.

10.2.17 Interferon (IFN) Gene Expression

Blood samples and a skin biopsy for analysis of Type 1 and Type 2 IFN gene expression profiles will be obtained at the time points specified in the SOE in Section 3. Guidance on performing the skin biopsy is provided in Section 10.2.7 and in the SRM.

10.2.18 Histology

A second skin biopsy will be obtained for histology analysis at the same time points as the IFN skin biopsies, as specified in the SOE in Section 3. Guidance on performing the skin biopsy is provided in Section 10.2.7 and in the SRM.

10.2.19 Serum Cytokines

Blood samples for analysis of DM-relevant cytokines/chemokine levels (including IL-6, IL-8, IP-10, I-TAC, MCP-1, MCP-2, and TNF α ; additional or alternative cytokines or chemokines may be assessed) will be obtained at the time points specified in the SOE in Section 3. The appropriate Laboratory Manual should be referenced for procedures on sample collection, handling, storage and shipping.

10.2.20 Immunogenicity

Blood samples for assessment of antibodies to IMO-8400 and dsDNA will be collected at the time points specified in the SOE in Section 3. The appropriate Central Laboratory Manual should be referenced for procedures on sample collection, handling, storage and shipping.

10.2.21 Vital Signs

Vital signs (temperature [oral or tympanic], pulse rate, respiratory rate, and blood pressure) will be measured at the time points specified in the SOE in Section 3. Vital signs will be measured prior to injection. All assessments will be performed after patients have remained seated for 5 minutes. Temperature should be recorded in degrees Celsius (°C), and pulse rate and respiratory rate should be measured over 1 minute.

10.2.22 Concomitant Medications/Therapies/Procedures During Treatment

Review of all concomitant medications, therapies and procedures, and changes in dosage of concomitant medications will be assessed at each visit as specified in the SOE in Section 3. Data on pharmacological and non-pharmacological treatments will be recorded on an eCRF page. At

each study visit, the patient will be asked about any additional treatments or any changes in regimen or dosages since the last visit. Indications for any new medications or therapies during the study period will be recorded as an AE. Further detail on concomitant medications is provided in Section 9.

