For the patient to be eligible, the result of the diagnostic evaluation should include a negative chest image and 1 of the following: a) a PPD skin test with \leq 5-mm induration, b) a negative (not detected) QuantiFERON result, or c) a negative T-SPOT.TB blood test. If the QuantiFERON result is indeterminate, the test may be repeated once. If the repeat QuantiFERON test is indeterminate, then a PPD skin test may be used to confirm patient eligibility. The PPD skin test is not an acceptable method of TB testing in Sweden.

9. Women of childbearing potential and men must agree to use effective contraceptive methods from Screening throughout the study and until at least 4 weeks after the last dose of study drug.

Non-childbearing potential is defined as a female who meets ***either*** of the following criteria: a) postmenopausal state defined as no menses for 12 months without an alternative medical cause or b) documented hysterectomy, bilateral tubal ligation, or bilateral oophorectomy.

Effective contraception methods that can achieve a failure rate of $<1\%$ per year when used consistently and correctly are considered highly effective birth control methods. Such methods are defined as ***I*** of the following:

- a) True abstinence, defined as refraining from heterosexual intercourse, when this is in line with the preferred and usual lifestyle of the subject. Periodic abstinence (e.g., calendar, ovulation, symptothermal, post-ovulation methods), declaration of abstinence for the duration of a trial, and withdrawal are not acceptable methods of contraception.
- b) Vasectomized partner (if that vasectomized partner is the sole sexual partner of the woman of childbearing potential and has received medical assessment of the surgical success of the vasectomy)
- c) An intrauterine hormone-releasing system (IUS)
- d) Oral, intravaginal, or transdermal combined (estrogen and progesterone) implanted hormonal contraceptive
- e) NOTE: For patients in Sweden, low dose oral contraceptives are not permitted
- f) An intra-uterine device (IUD)

10. Agrees to use a broad-spectrum (UVA/UVB) sunscreen with an SPF ≥ 15 daily (or a water-resistant, broad spectrum sunscreen with an SPF ≥ 30 for extended outdoor activity), and agrees to not increase their normal sun exposure during the course of this study.

11. Is willing and able to comply with this protocol.

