10.2.7 Skin Biopsy

Skin biopsies will be performed at the Baseline Visit 2/Week 1, Day 1, and at the EOT Visit 26/Week 25. Two 4 mm punch biopsies will be taken side by side on the upper back or upper arm of patients (whichever the Investigator feels has the most active skin disease at baseline) at baseline and in an adjacent area at the EOT biopsy. Sites where the baseline biopsy samples were taken should be photographed **PRIOR** to the baseline biopsy (no photographs will be taken after the biopsy) to document the disease activity and to guide the EOT biopsy site. Biopsies can be performed with or without local anesthesia, as considered appropriate for a specific patient or study site. The skin samples should be prepared for analyses as per the procedures described in the Laboratory Manual. The skin biopsy is not required for a premature discontinuation visit.

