11.1 Definition of Adverse Events

11.1.1 Adverse Event (AE)

An AE is any untoward medical occurrence in a clinical study patient, whether or not the event is considered causally related to the investigational product. An AE can be a new occurrence or an existing process that increases significantly in severity or frequency.

Adverse events include:

- Symptoms described by the patient or signs observed by the Investigator or medical staff
- Test abnormalities (laboratory tests, ECG, x-rays, etc.) that result in an alteration in medical care (diagnostic or therapeutic)
 - Abnormally low values for C3, C4 or A:G ratio may result in discontinuation of study treatment. Patients who discontinue due to these laboratory test abnormalities will be classified as “withdrawals due to adverse events” and a narrative describing their history and reason for withdrawal will be prepared by the Investigator.
 - Abnormally low eGFR or platelet count or abnormally high urine protein as described in Table 3 may result in discontinuation of study treatment. Patients who discontinue due to these laboratory test abnormalities will be classified as “withdrawals due to adverse events”.
- Injury or accidents. Note that if a medical condition is known to have caused the injury or accident (a fall secondary to dizziness), the medical condition (dizziness) and the accident (fall) should be reported as 2 separate AEs. The outcome of the accident (hip fracture secondary to the fall) should be recorded in source documents.

Abnormalities present at Baseline are considered AEs only if they reoccur after resolution or worsen in severity or frequency during the study.

Each AE is to be classified as serious or nonserious.

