11.2 Evaluation of Adverse Events

All AEs/SAEs experienced by the patient will be recorded in the eCRF and will include a concise description of: the event; date and time of event onset and resolution; relationship to study drug; severity; management of study medication; management of the AE/SAE, and outcome as described in Sections 11.2.1 through 11.2.7.

Abnormalities in vital signs, laboratory results, and other safety assessments will be recorded as an AE if they meet the definition of an AE (Section 11.1).

When possible, a diagnosis should be recorded as an AE, rather than symptoms or isolated laboratory abnormalities related to that diagnosis.

A medical or surgical procedure is not an AE; rather the condition leading to the procedure should be recorded as the AE. If the condition is not known, the procedure must be reported as an AE instead.

Similarly, death is not an AE, but is rather the outcome of the AE(s) that resulted in death. If the AE(s) leading to death are not known, then death must be reported as an AE.

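### Section 10.2.22 records the indication for any new medication or therapy as an AE, which is wider than the AE definition in Section 11.1.1 and can add non-events to the overall AE counts

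*Protocol*

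**What the plan says.** Section 10.2.22 governs what sites ask and record about concomitant treatment at each visit. It covers both drug and non-drug treatment and ends with the instruction "Indications for any new medications or therapies during the study period will be recorded as an AE". Its only cross-reference is to Section 9, which does not qualify that instruction.

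Section 11.1.1 defines the term: "An AE is any untoward medical occurrence in a clinical study patient", whether or not it is thought to be caused by the product. On conditions that patients bring into the trial it adds: "Abnormalities present at Baseline are considered AEs only if they reoccur after resolution or worsen in severity or frequency during the study".

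Section 11.2 gives the recording rules. Vital sign, laboratory and other safety abnormalities are recorded as AEs only when they satisfy Section 11.1. For procedures: "A medical or surgical procedure is not an AE; rather the condition leading to the procedure should be recorded as the AE". It has no matching sentence for medications.

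AEs are listed among the primary safety and tolerability endpoints in Section 6.1.1.1; the synopsis words the item as the frequency and severity of AEs. Section 11 starts AE collection at consent and ends it at the End-of-Study Visit.

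**The concern.** Sections 10.2.22 and 11.1.1 both tell sites what to enter as an AE, and for some ordinary situations a site cannot obey both. A patient with a stable condition at Baseline who starts a new drug for it has an AE under Section 10.2.22 and none under Section 11.1.1. A patient who receives a preventive treatment has an indication, namely prevention, that is not untoward at all.

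Two things are at stake. Non-events may enter the overall AE count and the proportion of patients with any AE. Sites may also resolve the conflict differently, so that the recorded count depends on the site as well as on the patient. Every AE also needs an investigator causality assessment (Section 11.2.3) and a severity grade (Section 11.2.4), and neither has a sensible answer for prophylaxis. Because the rule acts at data capture, a later analysis plan cannot easily separate such entries from real events.

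**Working it through.** The protocol gives no figure on this point, so there is none to reproduce. The check is a comparison of rules, followed by an illustration on assumed rates.

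**Comparison of the rules**

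| Situation | Section 10.2.22 | Sections 11.1.1 and 11.2 |
|---|---|---|
| New drug for a new illness | AE | AE |
| New drug for a Baseline condition that has worsened | AE | AE |
| New drug for an unchanged Baseline condition | AE | Not an AE |
| Non-live vaccine (Section 9.3 bans live vaccines; Section 9.1 leaves other treatments to the investigator) | AE | Not an AE: nothing untoward has occurred |
| Local anesthetic for a protocol biopsy (optional, Section 10.2.7) | AE on a literal reading | Not an AE: the procedure is excluded, and the disease behind it was present at Baseline |

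The rules agree in the first two rows, which are likely to cover most new medications. They conflict outright in the third and fourth. In the fifth, Section 11.2 points to the answer but Section 10.2.22 does not refer to it.

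**Direction of the effect (illustration only)**

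Let p be the true proportion of patients with at least one AE and q the proportion with at least one non-event recorded as an AE, taken as independent of p and equal in both arms. Then

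- recorded incidence = 1 − (1 − p)(1 − q)
- recorded risk difference = (p_active − p_placebo)(1 − q)

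The protocol gives neither p nor q. Taking p as 40% on placebo and 70% on active, a true difference of 30 points:

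| q | Placebo | Active | Difference |
|---|---|---|---|
| 0% | 40% | 70% | 30 points |
| 10% | 1 − 0.6 × 0.9 = 46% | 1 − 0.3 × 0.9 = 73% | 27 points |
| 25% | 1 − 0.6 × 0.75 = 55% | 1 − 0.3 × 0.75 = 77.5% | 22.5 points |
| 50% | 1 − 0.6 × 0.5 = 70% | 1 − 0.3 × 0.5 = 85% | 15 points |

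With 60% and 90% as the true rates the differences are the same: 30, 27, 22.5 and 15 points. In a group of 12 (Section 14.2), q = 25% in the 40%/70% case moves the expected number of patients with an AE from 4.8 to 6.6 on placebo and from 8.4 to 9.3 on active.

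The table shows direction only: counts rise and, if q is equal across arms, the contrast in overall incidence shrinks. It does not estimate what will happen in this trial.

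**The case against.** The strongest case on the other side has four parts.

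1. *Section 10.2.22 concerns the indication, not the treatment.* It can be read as a prompt to look for the condition behind a new drug, just as Section 11.2 does for procedures. This is fair, and it weakens the biopsy example. It does not help where the indication is itself an unchanged Baseline condition or pure prevention, and the sentence is worded as an instruction to record.

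2. *Section 11 is the dedicated AE section, and a sensible site would follow it.* Probably many would. But nothing in the protocol says that Section 11 prevails, and Section 10.2.22 does not refer to it.

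3. *The harm is limited.* This stands. Section 14.4.5 makes safety analyses descriptive, without testing. Section 14.4.5.3 tabulates AEs by event, severity and relationship, so a stray entry would appear under its own term and leave the rate of any specific event unchanged. Injection site reactions, laboratory results, vital signs and ECGs are untouched.

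4. *Divergence between sites is not demonstrated.* This also stands. Completion guides and the Study Reference Manual may already settle the matter. The protocol only permits divergence.

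A reader might go further and infer that the two biopsies alone create 36 × 2 = 72 spurious AEs, or that the Baseline biopsy makes the proportion with any AE 100% in every arm. The protocol does not support either figure. Anesthesia is optional: "Biopsies can be performed with or without local anesthesia, as considered appropriate for a specific patient or study site". No biopsy is required at an Early Termination Visit; with 10 of 12 patients per group completing, as Section 14.2 plans, there would be about 36 + 30 = 66 biopsy visits. The Baseline biopsy precedes the first dose, and whether pre-dose entries are tabulated is normally left to the SAP.

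A reader might likewise count contraception and sunscreen as one or two more AEs per patient. The protocol requires contraception from Screening, accepts some methods that are not medications, and exempts women of non-childbearing potential. Products already in use are not new, and the heading of Section 10.2.22 refers to the treatment period.

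**Conclusion.** The point holds as an internal contradiction in a recording rule. Section 10.2.22 is wider than the definition in Section 11.1.1, and nothing in Sections 9 or 11 narrows it. The clear conflicts are new treatment for an unchanged pre-existing condition and preventive treatment such as a non-live vaccine.

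Its size cannot be derived from the protocol and is probably small. The effect is confined to overall AE counts and overall AE incidence, which are part of the primary safety endpoint. No hypothesis test, error rate or event-specific rate is affected. That the contrast between arms would shrink depends on spurious entries being about equally common in each arm, which blinding makes plausible but the protocol does not establish. This is a minor point, worth correcting because the correction is so cheap.

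**What to change.** Replace the sentence in Section 10.2.22 with: *The indication for any new medication or therapy will be recorded on the concomitant medication page; it will be reported as an AE only if it meets the definition in Section 11.1.1. Prophylaxis, medication given for a protocol procedure, and unchanged pre-existing conditions are recorded as the indication and are not AEs.*

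The cost is one sentence in the protocol and a small update to the eCRF completion guide, so that the concomitant medication page accepts an indication that is not linked to an AE. Sites still record every indication, so no information is lost, and no dose, schedule or clinical rule changes.
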